10.2.2 Procedure for Reporting Serious Adverse Events

SAEs occurring from ICF signature until Safey visit at Day+1 are to be reported to Guerbet Pharmacovigilance department.

The investigator **must immediately** forward to Guerbet Pharmacovigilance department a duly completed SAE report form provided by Guerbet with study documents, even if it is obvious that more data will be needed in order to draw any conclusion:

- **By Fax #:** [name]
- **Or by e-mail to:** [contact]

In case of emergency, Guerbet Pharmacovigilance department may be contacted at: **[name].**

Additional information (e/g. autopsy, lab reports...) may be required by the Sponsor in a timely fashion to ensure accurate follow-up and assessment of each case and should be forwarded, anonymized, with a new form specifying basic information (follow-up number, subject details and number, adverse event, study product, causal relationship) and the new information.

The initial and follow up reports shall identify the study subject by his/her Identification Number assigned for the purpose of the study.

In order to allow the assessment and eventual subsequent regulatory reporting of the case, the following minimum information should be filled in:

- Subject's details including age, sex and subject's study enrolment number
- Subject's medical history relevant to the assessment of the event
- Type of event by reporting a diagnosis or if not available, symptoms
- Date and time to onset of the event
- End date of the event (will be reported in a follow-up report if the event is still ongoing at the time of first notification)
- Name of the investigational drug or procedure, date and time of administration, dose and volume administered
- Causal relationship to the investigational drug or procedure (mandatory)
- Outcome at the time of reporting

Any event leading to a SAE report should be reported in the medical file and in the adverse event section of the Case Report Form as requested in [Section 10.1.2](#).

SAEs should be followed up by the investigators until complete recovery of the subject or, if not possible, until stabilization of sequelae. The investigator may be requested by Guerbet to provide follow-up information in order to comply with current regulations as well as for comprehensive assessment purposes.

In addition, if occurring after the end of the subject's follow-up period defined for this study, events, serious or not, that the Investigator thinks may be associated with the study medication/procedure must be reported to the sponsor regardless of the time between the event and the end of the study.

SAEs associated with study procedures are to be notified using the same reporting procedure as described above.

According to local requirements, Guerbet or its representatives will communicate relevant safety information to the appropriate agency(ies), IEC and/or all active investigators, as it becomes available.

 CONFIDENTIAL	Protocol No. GDX-44-008 Version No.4.0 including amendments 1 and 2 12 December 2017	Page 46 / 64
---	--	--------------

The transmission of the information to the sponsor does not release the investigator from his responsibility to inform the regulatory authorities, if applicable.

10.3 Pregnancy and Adverse Events of Special Interest

In addition to the above adverse events, the special situations described below should be handled with the same procedure as the SAE reporting procedure.

10.3.1 *Pregnancy*

Any pregnancy (with or without an adverse event of women participating in the study and partners of men participating in the study) that occurs during the study and up to 7 days post P03277 administration must be reported to Guerbet via the SAE Report Form

Any participating subject who becomes aware of a pregnancy (subject's or subject's partner) during study participation should inform immediately the investigational site. The female subject should be immediately withdrawn from IMP administration.

Pregnancy will be monitored until completion or termination. If the pregnancy continues to term, the outcome (health of infant up to 8 weeks of age) will be reported to Guerbet using specific forms 'history and start of pregnancy" and "course and outcome of pregnancy" that will be provided by the pharmacovigilance. Any complication of pregnancy will be reported as an AE or SAE, as appropriate.

10.3.2 *Adverse Events of Special Interest*

An Adverse Event of Special Interest (AESI) is an AE designated by Guerbet for transmission to Pharmacovigilance in the same time frame as an SAE.

The AESI for this protocol is the following: Nephrogenic Systemic Fibrosis (NSF).

10.4 Other important safety issue /New fact

Any safety issues that may alter the current benefit-risk assessment of an investigational medicinal product, or would be sufficient to consider changes in the study drug administration or would involve any update of study documents or in the overall conduct of the study should be evaluated by the sponsor. It includes any new event likely to affect the safety of the subjects and that may be related to the conduct of the study or the development of the study drug such as:

- A SAE which could lead to the modification of the conduct of the study
- A significant hazard to the subject population such as lack of efficacy of an IMP used for the treatment of a life-threatening disease (if applicable).
- A new major finding from an animal study,
- A temporary halt of a trial for safety reasons if the trial is conducted with the same investigational medicinal products in another country by the same sponsor,
- Recommendations of the DMC, if any, where relevant for the safety of subjects,
- Any serious adverse reaction, expected or not, involving healthy volunteers.

According to local requirements, Guerbet or its representatives will communicate relevant safety information to the appropriate agency(ies), IEC and/or all active investigators, as it becomes available.

It might require other action, such as:

- urgent safety measures and their notification

Guerbet  CONFIDENTIAL	Protocol No. GDX-44-008 Version No.4.0 including amendments 1 and 2 12 December 2017	Page 47 / 64
--	--	--------------

- substantial amendments
- early termination of the trial

10.5 Unblinding Procedures

Not applicable

 CONFIDENTIAL	Protocol No. GDX-44-008 Version No.4.0 including amendments 1 and 2 12 December 2017	Page 48 / 64
---	--	--------------

11. PREMATURE DISCONTINUATION OF THE STUDY

11.1 Premature Discontinuation of the Study per Guerbet Decision

Guerbet reserves the right to discontinue the study at any time for medical, administrative or other reasons.

Guerbet will inform the relevant authorities in each country, the ethics committees, the study site investigators, pharmacists and hospital authorities according to the regulatory texts in force.

11.2 End of Study Participation for a Subject

Screening failures: Subjects who signed the informed consent form and discontinue before P03277 administration will be considered screening failures.

Criteria for premature discontinuation of subjects:

- eGFR < 60 mL/min/1.73m² at local blood sample screening;
- Adverse event (according to the investigator's judgment);
- Withdrawal of subject's consent;
- Subject lost to follow-up (date of last contact will be documented in the medical file and the CRF). Any effort will be undertaken to know the reason for this loss to follow-up and/or to exclude any adverse reaction as this reason. This will be documented in the medical file;
- Any treatment or medical procedure (e.g. chemotherapy, radiotherapy) during the study period;
- At the discretion of the investigator if the subject safety or well-being is not compatible with study continuation;
- Examination for standard of reference not available.

The data to be reported in the CRF for subjects subsequently discontinuing from the study are detailed in the protocol [section 15.3.2](#).

Subjects prematurely discontinuing the study will be replaced. It is expected to have around 3 subjects

 CONFIDENTIAL	Protocol No. GDX-44-008 Version No.4.0 including amendments 1 and 2 12 December 2017	Page 49 / 64
---	--	--------------

12. STATISTICAL ANALYSIS

The following section summarizes the statistical analysis method, which is fully described in the Statistical Analysis Plan.

12.1 Subjects Included in the Analysis

There will be four subject sets defined for this study: All subjects set, the Safety Set (SS), the Full Analysis Set (FAS) and the Per-Protocol Set (PPS).

All subject set will include all subjects with available data. This set will be used for subject disposition summaries and individual listings.

The Safety Set will include all subjects, receiving at least one injection of P03277, regardless of the quantity. This set will be used for evaluation of safety and description of demographic data and baseline characteristics.

The Full Analysis Set will include all subjects who undergone P03277 imaging and a standard of reference completed. This set will be used for evaluation of efficacy.

The Per Protocol Set will be a subset of the FAS and will include all subjects who have no major protocol deviations throughout their whole study period. Major deviations will be defined as having an impact on the primary efficacy criteria (e.g. P03277 wrong volume administered to the subject differing of more than 10% from the calculated one). Primary analysis will be repeated on this set.

12.2 Demographic and Baseline Data

Demographic parameters are age, sex, childbearing potential, body weight, height, and body mass index (BMI), ethnic origin (self-reported race/ethnicity). Baseline characteristics are the subject's history (including the medical history, intolerance history), the physical examination, chronic liver disease status at inclusion, documentation of suspected nodules, and the concomitant treatments on going at the time of screening/inclusion and before administration of P03277.

Summary statistics (number [n], mean, standard deviation [SD], median, minimum, and maximum) will be calculated for age, body weight, height and BMI and displayed by dose and overall. Frequency and percentages will be calculated for sex, subject chronic liver disease status at inclusion, and concomitant treatments on going at the time of screening/inclusion and ended before administration of P03277. These parameters will be displayed by dose and overall.

Subject's medical history will be coded using the MedDRA dictionary and tabulated by dose body system, preferred term and status (concomitant or not) and presented overall as well.

Subject's concomitant treatments will be coded using the Anatomical Therapeutic Chemical (ATC) Drug dictionary and tabulated by dose ATC code and presented overall as well.

12.3 Efficacy Data

Efficacy data will be summarized and presented by dose using the FAS and PP set for primary efficacy analysis and only using FAS for any other efficacy analysis.

Primary efficacy analysis

First of all, results of **examinations results used for standard of reference** will be presented: at subject level showing number and frequency of AFP results by category ($>200\text{ng/mL}$ or $\leq200\text{ng/mL}$) and by number of nodules for a subject (multiple or single nodule), previous contrast enhanced imaging modalities (CT and/or MRI), timelines and type of contrast agent category for MRI. At nodule level, typical imaging hallmark obtained by nodule (CT and/or MRI) and intensity of parenchyma relative to the nodule at each available phase will be presented. Timelines for biopsy (or surgical specimen collection) will be presented at subject level and nodules histology results (HCC, other malignant, regenerative or dysplastic nodule, benign, uncertain) will be presented at nodule level.

P03277 imaging diagnosis (HCC and not HCC) will be presented at nodule level displaying number and frequency for each standard of reference group HCC or not HCC according to the **Table 2**.

Table 2 : Diagnostic value evaluation for HCC

		P03277 imaging expert reading results			
		HCC: (Typical features on this MR examination)	Not HCC (No nodule/atypical features)		
Standard of reference	HCC:	True positive $n1$	False negative $n3$	Total $n1+n3$	
	Not HCC including uncertain cases	False positive $n2$	True negative $n4$	Total $n2+n4$	
		Total $n1+n2$	Total $n3+n4$	All total $N+$	

The following parameters will be calculated:

Sensitivity: the number of nodules showing true positive HCC divided by all nodules considered HCC according to standard of reference ($n1 / n1+n3$)

Specificity: the number of nodules showing true negative HCC divided by all nodules considered as not HCC or uncertain as standard of reference ($n4 / n2+n4$)

Accuracy: the number of nodules showing true positive HCC and true negative HCC over all nodules ($n1+n4 / N+$)

Positive predictive value: the number of nodules showing true positive HCC /all nodules showing HCC according to P03277 imaging ($n1 / n1+n2$)

Negative predictive value: the number of nodules showing true negative HCC /all nodules not showing HCC according to P03277 imaging ($n4 / n3+n4$)

 CONFIDENTIAL	Protocol No. GDX-44-008 Version No.4.0 including amendments 1 and 2 12 December 2017	Page 51 / 64
---	--	--------------

Secondary efficacy analysis

Technical adequacy of images

Technical adequacy will be presented by reading type (on-site or expert reading), by displaying number and frequency of adequate and inadequate images and the categories for inadequacy.

Visualization of biliary and liver vascular abnormalities

Biliary and liver vascular abnormalities will be presented globally, by displaying number and frequency of portal thrombosis, hepatic venous thrombosis, biliary tract invasion, and visualization of arterio-portal fistula.

Number of nodules detected

Number of nodules detected will be presented at subject level, showing number [n], mean, standard deviation [SD], median, minimum, and maximum.

Qualitative evaluation of nodule intensity and nodule description

Qualitative evaluation of nodule intensity (hypointensity, hyperintensity, isointensity and hetero/homogeneous) relative to parenchyma at each phase as well as, presence of capsule, visualization of fat, and iron presence will be presented by displaying number and frequency for each standard of reference group (HCC or not HCC/uncertainty).

Quantitative evaluation of nodule intensity

Quantitative evaluations of nodule intensity (SI, SNR, CNR, and PE) will be presented for each standard of reference group (HCC or not HCC/uncertainty) by displaying number [n], mean, standard deviation [SD], median, minimum, and maximum.

Quantitative evaluation of vascular intensity

Quantitative evaluations of aorta intensity and portal vein intensity (SI and SNR) will be presented globally and for each standard of reference group of subjects (subject with at least HCC or subject without any HCC) by displaying number [n], mean, standard deviation [SD], median, minimum, and maximum.

Qualitative evaluation at very delayed sequences for visualization of the parenchyma enhancement and nodule description

Qualitative evaluations for visualization of the parenchyma enhancement will be presented globally showing number and frequency at three available very delayed images and sequences (20mn, 1h, 2h). Qualitative evaluations for nodule enhancement relative to parenchyma will be presented by displaying number and frequency for each reference group (HCC or not HCC/uncertainty)

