The aim of GDX-44-008 study is to explore the diagnostic value for HCC of P03277 triphasic imaging of suspected nodules in patients with liver diseases. Some small HCC usually showing atypical features may be better seen and characterized under imaging with P03277. Participating subjects will not directly benefit from P03277 MRI. They will be diagnosed according to a combination of examinations for standard of reference including imaging and/or histology analysis

Guerbet  CONFIDENTIAL	Protocol No. GDX-44-008 Version No.4.0 including amendments 1 and 2 12 December 2017	Page 24 / 64
--	--	--------------

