7.1 Primary Criterion

For evaluation of **diagnostic value (defined as Sensitivity and Specificity) of P03277 for HCC** the following will be assessed:

Primary criteria:

- **Nodule diagnosis at P03277 imaging** (HCC, not HCC specify) will be assessed:
 - on a maximum of 3 hepatic nodules per subject
 - Based on visual qualitative analysis of P03277 triphasic imaging (arterial, portal and delayed phases) showing HCC typical hallmarks according to EASL/EORTC criteria (arterial hypervascularization and portal wash-out or delayed wash-out)
 - by two expert readers. In case of discordance, a consensus diagnostic will be obtained
- **The standard of reference** for diagnosing liver nodules (HCC, other malignant, regenerative or dysplastic nodule, benign, uncertain) will be given by the site according to their standard of care and according to adapted EASL/EORTC diagnostic criteria, considering previous contrast enhanced imaging (CT and/or MRI) and/or histology analysis and/or the more recent AFP results available:

HCC will be considered when:

- Histology is positive for HCC
- Or Nodule identified and characterized by typical features using two different triphasic contrast enhanced modalities. Typical features are arterial hypervascularization and portal wash-out or delayed wash-out

 CONFIDENTIAL	Protocol No. GDX-44-008 Version No.4.0 including amendments 1 and 2 12 December 2017	Page 33 / 64
---	--	--------------

- Or AFP>200ng/mL in a presence of a single nodule
 Other diagnosis than HCC could be based on imaging only and/or histology.

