8. NUMBER OF SUBJECTS

As a proof of concept study, no statistical test is planned. Subjects' data will be analyzed with descriptive statistics investigating the potential efficacy of P03277 in the liver for the diagnosis of HCC, by dose.

In total 40 subjects will be included:

- Firstly, 30 subjects in a first cohort with a P03277 dose of 0.1 mmol/kg
- Then 10 subjects in a second cohort with a P03277 dose of 0.05 mmol/kg

Number of subjects for the first cohort of the study is based on the hypothesis supported by a meta-analysis of several publications (8) that among the 30 subjects with suspected nodules, around 66% would have a HCC and the remaining subjects would be negative (liver nodule proven as a non HCC) and or uncertain after biopsy. Those hypothetic figures would help to estimate sensitivity and specificity values with the limitations expected for such small sample size.

It is considered that 10 subjects included in the second cohort will be sufficient to have an exploratory evaluation of the diagnostic value based on sensitivity and specificity.

 CONFIDENTIAL	Protocol No. GDX-44-008 Version No.4.0 including amendments 1 and 2 12 December 2017	Page 37 / 64
---	--	--------------

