9.1.3 Visit 3 – Day +1

During this visit, the following assessments or tasks will be performed:

- Use/change of **concomitant treatments** will be documented;
- **Blood samples for baseline haematology/biochemistry tests** will be collected according to central laboratory manual;
- **Vital Signs** (systolic and diastolic Blood Pressure in supine position, PR) should be recorded;
- **Injection-site tolerance** is to be evaluated;
- **Assessment of AEs** will be documented;
- **Proposed diagnosis as standard of reference** for each nodule (HCC, other malignant, regenerative or dysplastic nodule, benign, uncertain) should be assessed according to available evaluations (excluding histology and P03277 images) .

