9.1.4 Visit 4 – Optional (from 3 days up to 13 weeks)

Optionally, a biopsy will be done or surgically resected specimen will be collected at the time of loco-regional treatment and be analyzed for histology by local pathologist.

This procedure, whatever the type (biopsy or surgery), should be done between 3 days after P03277 administration to up to 13 weeks maximum. Alternatively it is acceptable to record results from histology done within 2 months prior to P03277 administration.

- **Examination results available for standard of reference diagnosis evaluation**
 - Date of nodule material collection (2 dates maximum)
 - Histological diagnosis per nodule : HCC, other malignant, regenerative or dysplastic nodule, benign, uncertain
- **Assessment of AEs that the investigator considers related to P03277 and/or study procedures.**

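### Table 2 counts nodules with an uncertain reference as not HCC, so finding a hidden HCC among them is scored as an error and missing it as a success

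*Protocol*

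**What the plan says.** The protocol collects the reference diagnosis in five categories, and uncertain is one of them. Section 9.1.3 asks for a proposed diagnosis "for each nodule (HCC, other malignant, regenerative or dysplastic nodule, benign, uncertain) should be assessed according to available evaluations", and section 9.1.4 records "Histological diagnosis per nodule : HCC, other malignant, regenerative or dysplastic nodule, benign, uncertain". Section 8 also separates the two kinds of nodule outside the HCC group: "the remaining subjects would be negative (liver nodule proven as a non HCC) and or uncertain after biopsy".

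Section 12.3 then merges them for the primary analysis. The second reference row of Table 2 is "Not HCC including uncertain cases", and specificity is "the number of nodules showing true negative HCC divided by all nodules considered as not HCC or uncertain as standard of reference". Sensitivity uses reference-HCC nodules only. The nodule-level secondary tables carry the same pooling, being laid out "for each standard of reference group (HCC or not HCC/uncertainty").

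The results are presented by dose. The primary analysis is repeated only on the Per Protocol Set (section 12.1).

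**The concern.** Uncertain means that the reference could not settle whether the nodule is HCC. Coding it as disease-negative fixes the score whatever the truth is: P03277 positive is a false positive, P03277 negative is a true negative. For a nodule that is in fact HCC, both scores are wrong.

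This touches the aim of the study. The rationale in section 1 is: "Some small HCC usually showing atypical features may be better seen and characterized under imaging with P03277". A small atypical HCC is also the kind of lesion that a reference based on earlier imaging may leave open. If it does, an agent that works as hoped loses specificity and positive predictive value (PPV), and an agent that misses the lesion is credited.

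Such nodules are plausible under the protocol's own rules. One earlier CT or MRI is enough for inclusion (section 4.1). The imaging route to a reference diagnosis of HCC needs two: "Or Nodule identified and characterized by typical features using two different triphasic contrast enhanced modalities" (section 7.1). Histology is optional (section 9.1.4), and the Day +1 reference diagnosis is made without P03277 images (section 9.1.3). Take a nodule that is typical on one earlier modality, with no histology and AFP not above 200 ng/mL. It meets none of the three HCC routes in section 7.1. If the site records it as uncertain and P03277 shows the same hallmark, Table 2 counts a false positive.

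Sensitivity and specificity are the primary criterion and the study is descriptive, so the content of these four cells is its main result.

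**Working it through.** **Inputs.** Cohorts of 30 and 10 subjects (section 8). About 66% with HCC, stated for the first cohort: 0.66 × 30 = 19.8, so about 20 HCC and 10 other. Carried to the second cohort as an assumption: 0.66 × 10 = 6.6, so about 7 and 3. Sensitivity 0.82 (any-sized lesions) and specificity 0.934 for extracellular agents are the meta-analysis values in section 1. Further assumptions: one nodule per subject, and the 66% read as reference-positive HCC. The number of uncertain nodules that are truly HCC (k) and the P03277 sensitivity in them (Se_u) are not in the protocol and are varied.

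**Specificity.** With nr nodules in the second row:

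coded specificity = [(nr − k) × 0.934 + k × (1 − Se_u)] / nr

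change per truly-HCC uncertain nodule = −(Se_u − 0.066) / nr

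| Se_u | nr = 10 (30 subjects) | nr = 3 (10 subjects) |
|---|---|---|
| 0.20 | −0.134/10 = −1.3 points | −0.134/3 = −4.5 points |
| 0.40 | −0.334/10 = −3.3 points | −0.334/3 = −11.1 points |
| 0.82 | −0.754/10 = −7.5 points | −0.754/3 = −25.1 points |

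Specificity falls whenever Se_u exceeds 1 − specificity, here 0.066.

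**All five measures**, 20 reference-HCC nodules, nr = 10, k = 1. For Se_u = 0.40 the coded cells are TP 16.4, FN 3.6, FP 9 × 0.066 + 0.40 = 0.994, TN 9 × 0.934 + 0.60 = 9.006. Against true status they are TP 16.8, FN 4.2, FP 0.594, TN 8.406.

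| Measure | Se_u 0.40: coded / true | Se_u 0.82: coded / true |
|---|---|---|
| Specificity | 0.901 / 0.934 | 0.859 / 0.934 |
| PPV | 0.943 / 0.966 | 0.921 / 0.967 |
| NPV | 0.714 / 0.667 | 0.705 / 0.690 |
| Accuracy | 0.847 / 0.840 | 0.833 / 0.854 |
| Sensitivity | 0.820 / 0.800 | 0.820 / 0.820 |

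PPV falls if a hidden HCC is detected. Negative predictive value (NPV) rises if one is missed. Accuracy changes by (1 − 2 × Se_u)/30 per nodule, so it rises below Se_u = 0.5 and falls above it.

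**Direction.** Let 2 of the 10 nodules in the second row be truly HCC, with specificity held at 0.934 in the other 8. An agent that misses both scores (8 × 0.934 + 2)/10 = 0.947. One that finds both scores (8 × 0.934)/10 = 0.747. An agent with perfect sensitivity and specificity scores 8/10 = 0.80.

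**Other assumptions.** With specificity 0.80 instead of 0.934, the loss per nodule at nr = 10 is (Se_u − 0.20)/10 = 0, 2.0 and 6.2 points. With two nodules per subject nr doubles and each loss halves, to 0.7, 1.7 and 3.8 points at specificity 0.934.

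**The case against.** The strongest reply is that the rule is explicit, fixed in advance and consistent across sections 8 and 12.3. Five categories at data capture and two at analysis are no contradiction, and the split can be read as HCC established versus not established. That is coherent as a grouping. It does not make the second row disease-negative, which is how the specificity and NPV formulas use it.

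The rule might also be called conservative. That holds for specificity and PPV when hidden HCCs are detected. It does not hold for NPV, nor in general for accuracy.

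Some of the reply stands. The pooling does not alter the sensitivity formula; the 2-point overstatement above arises because the reference leaves hard HCCs out of the denominator, and excluding uncertain nodules would not cure it. With 3 nodules in a denominator, one false positive moves specificity by 33 points under any coding, so much of the fragility in the 10-subject cohort is sample size. AFP above 200 ng/mL with a single nodule is a third route to HCC, and subjects without reference examinations are discontinued and replaced (section 11.2); both may reduce the number of uncertain nodules. But uncertain is itself a permitted reference result, so neither that rule nor the Full Analysis Set definition removes it. No test or decision threshold depends on the figures.

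The histology table shows uncertain separately, and individual listings are planned, so no data are lost. Neither is a cross-tabulation of uncertain nodules with the P03277 result. Further sensitivity analyses may sit in the SAP, but the rule questioned here is written into the protocol.

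**Conclusion.** The concern holds and should be fixed before analysis. Following section 12.3 exactly, a truly-HCC nodule with an uncertain reference is scored the wrong way round in specificity, PPV, NPV and accuracy. The direct effect is on those four measures; sensitivity is overstated only if such nodules are harder to characterise than the rest.

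The size is illustrative. It rests on one nodule per subject, the 66% HCC share and the literature values, and above all on two quantities the protocol does not give: how many nodules end as uncertain and how many of those are HCC. One such nodule weighs about three times as much in the smaller cohort (10/3). No error rate or power is affected, because no test is planned.

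**What to change.** Give uncertain its own third row in Table 2, cross-tabulated with the P03277 result. Calculate specificity, PPV, NPV and accuracy on nodules with an established HCC or non-HCC reference. Beside that, report all five measures, including sensitivity, with all uncertain nodules taken as HCC and with all taken as not HCC (the present rule). Split the pooled secondary tables in the same way.

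Example: 16 of 20 HCC detected, 7 of 7 non-HCC correct, 3 uncertain of which 2 are read as HCC.

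| | Present rule | Uncertain excluded | All uncertain = HCC |
|---|---|---|---|
| Sensitivity | 16/20 = 80% | 16/20 = 80% | 18/23 = 78% |
| Specificity | 8/10 = 80% | 7/7 = 100% | 7/7 = 100% |
| PPV | 16/18 = 89% | 16/16 = 100% | 18/18 = 100% |
| NPV | 8/12 = 67% | 7/11 = 64% | 7/12 = 58% |
| Accuracy | 24/30 = 80% | 23/27 = 85% | 25/30 = 83% |

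The excluded-uncertain column drops the hardest nodules and can flatter the agent (its accuracy here lies above both assignments), so it must never stand alone. The two assignments are not the sharp limits for every measure, but the third row lets a reader work out any other.

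The cost is protocol and SAP wording, one table row and two extra calculations, with no new data. The price is a smaller specificity denominator, 7 instead of 10 in the example.
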